3.4.1.4 Subgroup Analyses

Two subgroup analyses will be performed if there are at least 6 subjects in the smallest subgroup. The analysis will be an analysis of covariance with fixed effects for treatment (MEDI0382 or Placebo), subgroup, and treatment by subgroup interaction with the baseline AUC used as a covariate. The subgroups that will be included in the analysis are:

- Insulin strata (insulin dose ≥ 20 U/day and insulin dose < 20 U/day)
- Baseline HbA1c category ($< 8\%$ and $\geq 8\%$)

3.4.2 Secondary Efficacy Endpoint(s) and Analyses

3.4.2.1 Secondary Efficacy Endpoint(s)

- Change in HbA1c from baseline (Day 1) to the end of 32 days of treatment (Day 32)
- Change in fasting glucose from baseline (Day 1) to the end of 32 days of treatment (Day 32)
- Change in percentage of time spent within a target glucose range of 70 mg/dL (3.9 mmol/L) to 180 mg/dL (10 mmol/L) over a 7-day period at baseline (Days -8 to -2) to the final week of treatment (Days 26-32)

- Percentage and absolute change in body weight from baseline (Day 1) to the end of 32 days of treatment

3.4.2.2 Handling of Dropouts and Missing Data

If the end of treatment evaluation is missing for weight, the last post-baseline value will be used in the analysis (LOCF). Subjects who do not have a valid end of treatment evaluation for fasting plasma glucose, HbA1c, or percentage of time CGM glucose within target range will not be included in the analysis.

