2.2 Secondary Objectives and Associated Endpoints

Table 2 Secondary Objectives and Associated Endpoints

Type	Objective	Endpoints
Safety	To characterise the safety profile and tolerability of MEDI0382 titrated up to a dose level of [REDACTED] during dosing and follow-up in subjects with T2DM and renal impairment	
 Measures of safety and tolerability (adverse events/serious adverse events [AEs/SAEs], vital signs, postural blood pressure [BP] changes, electrocardiogram [ECG], laboratory test results) Change in mean 24-hour pulse rate, systolic and diastolic blood pressure from baseline (Day -5) to the end of dosing at each dose level (Days 4, 11, 18, and 32)
Efficacy	To assess the effects of MEDI0382 titrated up to a dose level of [REDACTED] on additional measures of glycaemic control versus placebo after 32 days of treatment	
 Change in haemoglobin A1c (HbA1c) from baseline (Day 1) to the end of 32 days of treatment (Day 32) Change in fasting glucose from baseline (Day 1) to the end of 32 days of treatment (Day 32) Change in percentage of time spent within a target glucose range of 70 mg/dL (3.9 mmol/L) to 180 mg/dL (10 mmol/L) over a 7-day period at baseline (Days -8 to -2) to the final week of treatment (Days 26-32)
Efficacy	To assess the effects of MEDI0382 titrated up to a dose level of [REDACTED] on weight versus placebo after 32 days of treatment	
 Percentage and absolute change in body weight from baseline (Day 1) to the end of 32 days of treatment (Day 33)

Table 2 Secondary Objectives and Associated Endpoints

Type	Objective	Endpoints
PK/Immunogenicity	To characterise the PK profile and immunogenicity of MEDI0382	
• PK endpoints: AUC over a dosing duration, maximum observed concentration (C_{max}), time to C_{max} (T_{max}), trough plasma concentration (C_{trough})• Development of anti-drug antibodies (ADA) and titre (if confirmed positive)

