4.1.5 Withdrawal from the Study

Subjects are free to withdraw their consent to participate in the study (investigational product and assessments) at any time, without prejudice to further treatment. Subjects who withdraw consent will be asked about the reason(s) and the presence of any adverse events (AEs) and will be encouraged to remain in study for the remainder of the scheduled follow-ups. Adverse events will be followed up; diary cards and all study medications should be returned by the subject. If a subject withdraws from further participation in the study, then no further study visits or data collection should take place.

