- i Dosing will occur daily from Day 1 to Day 32 inclusive. Subjects are required to be dosed at the clinic for the [REDACTED] dose and on study day visits when predose procedures are required (Days 5, 12, 19, and 32). See Section 4.3 for further information. Ideally subjects should self-administer doses under supervision and study site staff should ensure that the subject self-administers the first dose of IP delivered via PFS on Day 5 to ensure that they are confident in self-injecting via PFS at home.
- j Up-titration steps will be performed on Day 5 (dose will increase from [REDACTED]), Day 12 (dose will increase from [REDACTED]) and Day 19 (dose will increase from [REDACTED])
- k PK Sampling Schedule for MEDI0382:
 - Day 1: Predose
 - Day 5: Predose
 - Day 12: Predose
 - Day 19: Predose
 - Day 32: Predose and at 0.5, 1, and 2 hours (\pm 15 min); 4, 6 and 8, (\pm 30 min) postdose
 - Day 33: 24 hours (\pm 15 min) postdose
- l Samples will be collected for potential future metformin PK analysis only in subjects who are taking metformin (metformin PK samples are to be taken prior to metformin dose administration and therefore subjects should be advised to delay their morning metformin dose until after this blood test on these study visits.)
- m ADA sampling schedule: Day 1 predose; Day 12 predose; Day 32 predose
- n During the informed consent process subjects will be asked to provide consent for the main study [REDACTED] Only sample(s) for which the subject has consented will be taken.

- o MMTT schedule: Following a minimum 8-hour fast overnight and where relevant, 2.5 hours after taking the IP, a blood sample for glucose will be taken immediately prior (within 15 minutes) to the subject drinking one entire can of Ensure Plus as a standardised meal (ie, “0 minutes”). Blood samples for glucose will additionally be drawn at 15, 30, 45, 60, 90, 120, 180, and 240 minutes (± 5 min) after consumption of the standardised meal. [REDACTED]
- p A urine pregnancy test should be conducted on any female subject of childbearing potential as detailed in the schedule. Pregnancy tests do not need to be conducted in women who are surgically sterile (ie, bilateral tubal ligation, bilateral oophorectomy, or complete hysterectomy) or are postmenopausal (defined as at least 1 year since last menses and/or having an elevated follicle stimulating hormone laboratory value which is in the postmenopausal range in previous laboratory test results).

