4.2.3 Follow-up Period

Table 11 shows all procedures to be conducted during the follow-up period.

Table 11 Schedule of Follow-up Procedures

Study Period	Follow-up Period		
Visit Number	V10	V11	V12 (EoS) ^a
Procedure / Study Day	D33	D40 ± 5	D60 ± 5
Outpatient visit to the clinic	X	X	X
Physical examination (abbreviated)		X	X
Weight	X ^b	X	X
ECG		X	X
Vital signs		X	X
Collect blood for			
Serum chemistry (including eGFR calculation)	X	X	X
Fasting glucose			X
Calcitonin ^c			X ^b
Haematology		X	X
ADA ^d			X ^c
HbA1c			X
PK for MEDI0382 ^e	X		
Collect urine for			
Urinalysis (dipstick)		X	X
Urine albumin / creatinine ratio ^f	X	X	X
Pregnancy test (women of childbearing potential only) ^g	X		X
Check CGM readings [REDACTED]	X	X	
Removal of CGM sensor		X	
Glucose meter and diary provision	X	X	
Assessment of AEs / SAEs	X	X	X
Concomitant medications		X	X

AE = adverse event; ADA = anti-drug antibody; BMI = body mass index; CGM = continuous glucose monitoring; ECG = electrocardiogram; eGFR = estimated creatinine clearance; EoS = End of study; HbA1c = glycated haemoglobin; SAE = serious adverse event.

^a Subjects are required to fast for at least 8 hours overnight prior to the visit. [REDACTED]

- ^b D33 body weight should be measured in the morning prior to breakfast. Refer to Section 4.3.1.3 for details.
- ^c Calcitonin need only be re-measured in subjects who had a level > upper limit of normal (ULN) on Day 32
- ^d If this sample is ADA positive, the subject will be asked to return to provide another sample at approximately 3 months after the end-of-study visit (post-study sample). If this sample is ADA positive, additional visit(s) every 3 months should continue until a sample tests negative for ADA.
- ^e PK Sampling Schedule for MEDI0382:
 - Day 1: Predose
 - Day 5: Predose
 - Day 12: Predose
 - Day 19: Predose
 - Day 32: Predose and at 0.5, 1, and 2 hours (\pm 15 min); 4, 6 and 8 (\pm 30 min) postdose
 - Day 33: 24 hours (\pm 15 min) postdose
- ^f Urine sample for urine albumin / creatinine ratio should be taken as an early morning specimen during the first void of the day.

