3 STATISTICAL METHODS

3.1 General Considerations

Data will be presented in data listings sorted by insulin strata, treatment, subject number and date collected, where appropriate. Tabular summaries will be presented for each treatment and for insulin strata within treatment. Categorical data will be summarized by treatment and for insulin strata within each treatment with the number and percentage of subjects within each category. In general, continuous variables will be summarized by treatment and insulin strata within treatment with descriptive statistics including mean, standard deviation, median, minimum, and maximum. Safety variables will generally be summarized by treatment across insulin strata.

All available data will be included in the analyses and missing data will not be imputed except as specified in the calculation of the AUC values. Unless specified otherwise, baseline values will be defined as the last valid assessment prior to the first administration of study medication.

All statistical tests will be 2-sided at an alpha = 0.10 significance level unless stated otherwise. There will be no adjustment for multiplicity.

Data analyses will be performed using SAS[®] version 9.3 or higher (SAS Institute Inc., Cary, NC) in a UNIX environment. The analytical results generated from SAS programs will follow MedImmune SAS programming standards and will be validated according to MedImmune SAS validation procedures.

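### LOCF for missing weights (SAP 3.4.2.2) contradicts SAP 3.1 and can count a titration-phase weight as the Day 33 result; the bias can go either way

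*SAP*

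**What the plan says.** SAP 3.1 sets the general rule: "missing data will not be imputed except as specified in the calculation of the AUC values". Weight is not part of that exception.

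SAP 3.4.2.2 then sets a different rule for weight: "If the end of treatment evaluation is missing for weight, the last post-baseline value will be used in the analysis (LOCF"). The sentence after it goes the other way for the remaining secondary efficacy endpoints: "Subjects who do not have a valid end of treatment evaluation for fasting plasma glucose, HbA1c, or percentage of time CGM glucose within target range" are left out of the analysis. No reason is given for treating weight differently.

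The endpoint day is clear in the protocol and open in the SAP. Protocol 2.2 has "Percentage and absolute change in body weight from baseline (Day 1) to the end of 32 days of treatment (Day 33"). SAP 3.4.2.1 has "Percentage and absolute change in body weight from baseline (Day 1) to the end of 32 days of treatment", with no day number.

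Protocol Tables 10 and 11 schedule weights on Days 1, 5, 12, 19, 32 and 33, then at the two later follow-up visits. The Day 33 weight has its own instruction: "D33 body weight should be measured in the morning prior to breakfast". Dose increases fall on Days 5, 12 and 19 (Table 10, footnote j), and the last level covers the final 14 of the 32 dosing days (protocol synopsis).

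**The concern.** There are two problems. The first is textual: SAP 3.1 names one exception and weight is not it, so an analyst must break one section to follow the other. In a study of about 40 subjects, that choice should not be left until after unblinding.

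The second is what LOCF does in a titrated design. Under Protocol 4.1.5, "If a subject withdraws from further participation in the study, then no further study visits or data collection should take place". A subject who leaves after the Day 5 visit therefore has only a weight from the end of the first dose level, and LOCF enters it as the end-of-treatment result. A subject who stops the product but stays in the study normally gives a true Day 33 weight (Protocol 4.1.6). A subject who leaves before Day 5 has no post-baseline weight to carry. The analysed mean then mixes different quantities, and carried values count as observed ones.

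Superior weight loss is a stated secondary hypothesis (Protocol 1.7.2), so the comparison will be read. The primary analysis is not affected.

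**Working it through.** **Plan's own figure.** The documents give no power, effect size or SD for weight. The only stated power is for the primary endpoint (above 85%; 20 per arm, difference 18.1, SD 20, two-sided 0.10). It reproduces: 18.1 / (20 × √(2/20)) = 2.862, and 2.862 − 1.645 = 1.217, so power is 88.8% (87.8% with the t distribution). It says nothing about weight.

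**Inputs from the documents.** 20 per arm (SAP 2.4); weights on Days 5, 12, 19, 32 and 33 (Protocol Tables 10 and 11); two-sided alpha 0.10 (SAP 3.1).

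**Assumptions.** The weight effect grows linearly with days of dosing; a Day d weight reflects d − 1 doses and the Day 33 weight reflects 32; only active-arm subjects are carried; the target is the effect under full treatment.

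**Step 1: share of the effect present at the carried weight.** f = (d − 1)/32.

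**Step 2: expected LOCF difference as a share of the full Day 33 difference.** Ratio = 1 − (k/20)(1 − f), where k is the number of active-arm subjects carried.

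| Carried from | f | k = 1 | k = 2 | k = 3 |
|---|---|---|---|---|
| Day 5 | 0.125 | 0.956 | 0.912 | 0.869 |
| Day 12 | 0.344 | 0.967 | 0.934 | 0.902 |
| Day 19 | 0.563 | 0.978 | 0.956 | 0.934 |
| Day 32 | 0.969 | 0.998 | 0.997 | 0.995 |

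The smallest loss from Days 5 to 19 is 1 − 0.978 = 2.2% (one carry, Day 19). The largest is 1 − 0.869 = 13.1% (three carries, Day 5). From Day 32 it is at most 0.5%.

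**Step 3: variant with placebo weight loss.** Suppose the active arm loses L% and placebo 0.5%, so the full difference is L − 0.5. Each active carry removes L(1 − f)/20. For two Day 5 carries and one Day 12 carry:

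- L = 2: 2 × (0.875 + 0.875 + 0.656)/20 = 0.241 of 1.5 points, 16%.
- L = 3: 0.361 of 2.5 points, 14%.
- L = 4: 0.481 of 3.5 points, 14%.

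The share is larger than in Step 2 because the carried subject forgoes the placebo-type loss as well.

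**Step 4: power, if weight had 80% at 20 v 20 (assumed).** This corresponds to a standardised difference of 0.801 (noncentral t). Three carries from Days 5 to 19, allowing for the extra spread from mixing carried and full values, give 68.5% to 74.8%. Leaving those three out (17 v 20) gives 76.9%, provided they would have responded like the rest.

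**Step 5: the reverse direction.** If the carried subjects had already lost 1.5 times the full effect, for instance with vomiting, the ratio is 1 + (k/20)(0.5): 1.025, 1.050 and 1.075 for one, two and three carries. The difference is then inflated.

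**The case against.** A reader might infer that LOCF necessarily dilutes the weight comparison. The documents do not support that. Dilution needs loss that builds up over dosing, carries mainly in the active arm, and a target of the effect under full treatment. Step 5 shows the opposite case. An on-drug weight carried past stopping can also overstate the loss if the target is the actual Day 33 weight. This objection stands.

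Nor do the documents show that gastrointestinal intolerance will feed many subjects into LOCF. Protocol 4.1.6 makes it a reason to stop the product, and such subjects are followed for scheduled assessments, with listed exceptions. Many would have an observed Day 33 weight, so LOCF reaches mainly study withdrawals and missed visits. A missed Day 33 visit with a Day 32 weight is nearly harmless. Both points stand.

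A reader might also take the rule to admit a weight from the later follow-up visits (Day 40 or Day 60). That is strained: the SAP calls the method LOCF, and using a later value would carry it backward. It needs a clarifying word at most.

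The magnitudes depend on chosen scenarios. Up to three withdrawn subjects may be replaced (Protocol 4.1.7), and treated subjects stay in the ITT population. With 23 active subjects, the 14.4% at L = 3 becomes 14.4 × 20/23 = 12.5%. The effect on the standard error has not been calculated.

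Finally, a specific rule is often read as overriding a general one, so the analyst would probably apply LOCF. That would settle which rule is used, but not whether the rule is sound.

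**Conclusion.** The contradiction between SAP 3.1 and 3.4.2.2 stands on the text and needs no assumption. It also stands that the rule lets a Day 5, 12 or 19 weight from a withdrawn subject serve as the Day 33 result, treated as observed.

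The direction of bias is not established. Under linear build-up with active-arm carries only, one to three carries from Days 5 to 19 shrink the difference by about 2% to 13%. The variant with 0.5% placebo loss gives about 14% to 16% for three early carries. A carry from Day 32 is negligible. These are illustrations, because the weight effect, its SD and the dropout rate are all assumed.

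The point is worth correcting because it bears on a stated secondary hypothesis and the weights needed for a better analysis are already scheduled.

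**What to change.** - Delete the LOCF sentence in SAP 3.4.2.2, so that SAP 3.1 governs weight as it does the other secondary endpoints.
- State Day 33 as the weight endpoint day in SAP 3.4.2.1, matching Protocol 2.2.
- Estimate the Day 33 contrast, for percentage and absolute change, with a repeated-measures model on the observed scheduled weights up to Day 33. Include treatment, visit, treatment-by-visit and baseline weight. Pre-specify the covariance structure, since Day 32 and Day 33 weights will be almost collinear with about 20 subjects per arm.
- Support it with observed-case ANCOVA at Day 33, in line with Protocol 4.8.3.2. Keep LOCF at most as a sensitivity analysis.

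Cost: SAP wording and one extra model, with no new data. The main weight analysis would depart from Protocol 4.8.3.2, which asks for an ANCOVA similar to the primary one, and the SAP should say so. If that is unwanted, observed-case ANCOVA alone removes the contradiction, though it leaves the partial weights of withdrawn subjects unused.

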3.4.2.3 Secondary Efficacy Analyses

The secondary efficacy endpoints will be analyzed with ANCOVA, similar to that used for the primary endpoint.

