Statistical analyses: The primary efficacy analysis will be performed using the intent-to-treat (ITT) population. The primary efficacy endpoint, percentage change in MMTT glucose AUC from baseline (Day -5) to the end of 32 days of treatment will be analysed using an analysis of covariance (ANCOVA) model. The model will include fixed effect of treatment and baseline AUC as a covariate. The difference of the percent change in glucose AUC between the two treatment arms will be compared with a two-sided significance level of 0.10. Secondary efficacy analyses will be performed using the ITT population. All secondary efficacy endpoints will be summarised by visit and by treatment group. The change in percentage of time spent within a target glucose range of 70 mg/dL (3.9 mmol/L) to 180 mg/dL (10 mmol/L) over a 7-day period at baseline to the final week of treatment will be analysed using a Wilcoxon rank-sum test. All other continuous endpoints will be analysed using a similar ANCOVA model as that for the primary analysis.

Safety analyses will be performed using the as-treated population. AEs and SAEs will be coded by the most updated version of Medical Dictionary for Regulatory Activities (MedDRA), and the type, incidence, severity, and relationship to study investigational product will be summarised by MedDRA System Organ Class and Preferred Term and by treatment. AEs leading to discontinuation, AEs leading to death, and deaths will also be summarised. Specific AEs will be counted once for each subject for calculating percentages. In addition, if the same AE occurs multiple times within a particular subject, the highest severity and level of relationship observed will be reported. Subject-level data listings of all AEs will be presented. Other safety data, such as vital signs, clinical laboratory data, ECG, and physical examination findings will be descriptively summarised at each time point by treatment. Mean ambulatory blood pressure and pulse rate measurements recorded over 24 hours at different time-points will be analysed using an ANCOVA model, adjusting for treatment and measurement at baseline.

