4.8 Statistical Evaluation

4.8.1 General Considerations

Tabular summaries will be presented by treatment group. Categorical data will be summarized by the number and percentage of subjects in each category. Continuous variables will be summarized by descriptive statistics. Additional details of statistical analyses will be described in the statistical analysis plan. Analyses of secondary and exploratory efficacy variables will be performed without any adjustment for multiplicity.

Analysis Populations

Intent to Treat: The intent-to-treat (ITT) population is defined as all subjects that are randomised and receive any amount of investigational product, analysed according to randomised treatment assignment. All efficacy analyses will be performed on the ITT population unless otherwise specified.

As-Treated Population: The as-treated population is defined as all subjects who received at least 1 dose of investigational product and will be analysed according to the treatment actually received. All safety analyses will be performed on the as-treated population.

PK Population: The PK population includes all subjects who received at least 1 dose of investigational product and had at least one PK sample taken with a value above the lower limit of quantitation.

Immunogenicity Population: The Immunogenicity population includes all subjects in the as-treated population who have at least one serum immunogenicity result.

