4.8.3.2 Secondary Efficacy Analyses

Secondary efficacy analyses will be performed using the ITT population. All secondary efficacy endpoints will be summarised by visit and by treatment group. The change in percentage of time spent within a target glucose range of 70 mg/dL (3.9 mmol/L) to 180 mg/dL (10 mmol/L) over a 7-day period at baseline to the final week of treatment will be analysed using a Wilcoxon rank-sum test. All other continuous endpoints will be analysed using a similar ANCOVA model as that for the primary analysis.

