6.2.2 Study Agreements

The Principal Investigator at each/the centre should comply with all the terms, conditions, and obligations of the Clinical Study Agreement, or equivalent, for this study. In the event of any inconsistency between this protocol and the Clinical Study Agreement, the terms of protocol shall prevail with respect to the conduct of the study and the treatment of subjects and in all other respects, not relating to study conduct or treatment of subjects, the terms of the Clinical Study Agreement will prevail.

Agreements between MedImmune and the Principal Investigator must be in place before any study-related procedures can take place, or subjects are enrolled.

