7.4 Changes to the Protocol and Informed Consent Form

Study procedures will not be changed without the mutual agreement of the Principal Investigator and MedImmune.

Substantial changes must be documented in a study protocol amendment. MedImmune will distribute amended versions of the protocol to the principal investigator(s). Before implementation, amended protocols must be approved by relevant IRB/IEC (see Section 7.2)

and according to local requirements, the national regulatory authority approval. The IRB/IEC must also approve revisions to the informed consent form, advertising, and any other written information and/or materials resulting from the change to the protocol.

If local regulations require, any unsubstantial changes will be communicated to or approved by each IRB/IEC.

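### Change in CGM time in range has two planned tests, Wilcoxon in the protocol and ANCOVA in the SAP, and no explicit rule says which prevails

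*SAP*

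**What the plan says.** **Protocol.** The synopsis (Statistical analyses) and section 4.8.3.2 name a test for this endpoint. In 4.8.3.2 the change in time within the 70 to 180 mg/dL range from baseline "to the final week of treatment will be analysed using a Wilcoxon rank-sum test". The next sentence is: "All other continuous endpoints will be analysed using a similar ANCOVA model as that for the primary analysis". Time in range is thus a deliberate exception, stated in two places.

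**SAP.** Section 3.4.2.1 lists the same endpoint ("Change in percentage of time spent within a target glucose range"), with the same baseline window (Days -8 to -2) and final window (Days 26 to 32) as the protocol's secondary objectives. Section 3.4.2.3 consists of one sentence: "The secondary efficacy endpoints will be analyzed with ANCOVA, similar to that used for the primary endpoint". The primary model it refers to, in section 3.4.1.3, has a fixed treatment effect and the baseline value as covariate. The legible SAP text names no rank-based or other non-parametric test.

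**Level.** SAP section 3.1 sets all tests at two-sided 0.10 without multiplicity adjustment. Protocol section 4.8.1 also leaves the secondary analyses unadjusted.

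**The concern.** The two tests answer different questions. The rank-sum test compares the ranks of the unadjusted changes. ANCOVA estimates a difference in mean change adjusted for baseline. They give different p-values and different effect measures, and with 20 subjects per arm they can fall on opposite sides of 0.10.

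A programmer working from the SAP would run ANCOVA, while a reader of the protocol would expect Wilcoxon. Either result could be presented as the planned one. That leaves room to choose after the data are seen, which a pre-specified plan is meant to prevent.

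**Working it through.** **1. Does any text settle the order of the documents?**

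- Protocol 4.8.1: "Additional details of statistical analyses will be described in the statistical analysis plan". Replacing a named test is more than a detail, so this leans towards the protocol. It does not say what happens in a conflict.
- Protocol 7.4: "Substantial changes must be documented in a study protocol amendment". This also leans towards the protocol, but it does not define what is substantial.
- Protocol 6.2.2: "In the event of any inconsistency between this protocol and the Clinical Study Agreement, the terms of protocol shall prevail". This is the only precedence clause found, and it does not cover the SAP.
- Dates: the current protocol is Amendment 4 (12Nov2018), and SAP version 2.0 is dated 08June2018. The later document names Wilcoxon.
- Change records: no legible entry in protocol section 9 or SAP section 6 records a change of test.

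Three pointers favour Wilcoxon, but none is an explicit rule.

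**2. Is there a planned figure to reproduce?** Not for this endpoint. The only power statement concerns the primary endpoint: 20 per arm, difference 18.1, SD 20, two-sided 0.10. The standard error is 20 × √(2/20) = 6.32, so 18.1/6.32 = 2.86. Power is Φ(2.86 − 1.645) = 88.8% (87.8% with the t distribution). The stated figure of more than 85% is confirmed, but it has no bearing on time in range.

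**3. How much could the choice matter?** The documents give no mean, SD, correlation or effect for time in range, so every input here is assumed apart from the 20 per arm and the 0.10 level.

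- Settings: mean/SD of 60/15, 60/20, 60/25, 50/20 and 75/20; correlation between baseline and final week of 0.3, 0.5, 0.7 and 0.9; final-week errors normal or heavy-tailed (t with 3 df, scaled to unit variance). That is 5 × 4 × 2 = 40 settings.
- Effect: 0 or 10 points, added before values were clipped to 0–100. Clipping makes the realised gain somewhat smaller.
- Tests: rank-sum on change (normal approximation, continuity correction), and ANCOVA on change with treatment and baseline. There were 20,000 simulated trials per setting. The Monte Carlo standard error near 15% is √(0.15 × 0.85/20,000) = 0.25 points.

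Base case (60/20, normal errors):

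| Correlation | No effect: at least one test rejects | 10-point effect: tests disagree | Power, Wilcoxon | Power, ANCOVA |
|---|---|---|---|---|
| 0.3 | 14.9% | 24.4% | 34% | 48% |
| 0.5 | 14.0% | 21.3% | 43% | 55% |
| 0.7 | 13.6% | 16.4% | 59% | 68% |
| 0.9 | 12.6% | 3.1% | 95% | 96% |

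The first result column follows from P(at least one) = (P(Wilcoxon) + P(ANCOVA) + P(disagree))/2. At correlation 0.5 this is (9.4 + 9.9 + 8.6)/2 = 14.0%.

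Over all 40 settings with no effect, Wilcoxon alone rejects in 9.3% to 10.4% of trials, ANCOVA alone in 9.6% to 10.5%, and at least one of them in 12.4% to 16.0%. With the 10-point effect, ANCOVA has more power in 34 settings, by up to 19.3 points. Wilcoxon has more in 6, all heavy-tailed with correlation 0.7 or 0.9, by at most 4.5 points.

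**4. Context.** SAP 3.4.2.1 holds five secondary efficacy measures, each tested at 0.10. If they were independent (the two weight measures are not), the chance of at least one false positive would be 1 − 0.9⁵ = 41.0%. Letting one of the five rise to 12.4% or 16.0% gives 1 − 0.9⁴ × 0.876 = 42.5% or 1 − 0.9⁴ × 0.840 = 44.9%. Most of this comes from the decision not to adjust. The choice of test adds 1.5 to 3.9 points.

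**The case against.** The best reply is that the documents are not evenly balanced. The protocol singles this endpoint out by name, whereas the SAP has one generic sentence. The SAP is also visibly behind the protocol: its introduction cites Amendment 2, and its sections 2.2 and 4 still plan an interim analysis that the current protocol says is not planned. A careful reader would probably take Wilcoxon as the planned test, and a departure from it would be visible. This stands and limits the harm. It does not remove the conflict, because the SAP is the document the analysis is programmed from. Nor does its age explain the difference, since the listed changes in Amendments 3 and 4 do not touch the secondary analyses.

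SAP section 3.4.3 is redacted, and the statistical programming plan and the German local amendment are not available. Any of them could bear on the point. Section 3.4.3 is headed as other efficacy analyses, so it is an unlikely place for the main test of a secondary endpoint.

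The word similar in the SAP sentence cannot stretch to a rank test, because the sentence names ANCOVA.

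The simulated inflation needs someone to run both tests and report the favourable one, and nothing in the documents suggests that intention. That is correct. The figures show what the ambiguity permits and do not predict what will happen.

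**Conclusion.** The contradiction is plain in current, legible text: two different tests for one endpoint, with no explicit precedence rule. This conclusion does not depend on the simulation.

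The size is modest. It concerns one secondary endpoint with an unadjusted, nominal p-value. The primary analysis is ANCOVA in both documents, and the type of test agrees for HbA1c, fasting glucose and weight. Under the assumed inputs, a free choice between the tests moves a 10% error rate to 12.4%–16.0%. At moderate correlation (0.5) with a 10-point effect, the choice changes the significance verdict in about one base-case trial in five. The plan should be corrected, but the main conclusion of the trial is not at risk.

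**What to change.** Before unblinding, extend the sentence in SAP 3.4.2.3 with: *except change in CGM time in range, for which the Wilcoxon rank-sum test is the main analysis, as in the protocol, and ANCOVA with treatment and baseline time in range is a sensitivity analysis.* A rank test alone gives no effect measure, so the clause should also name the estimate to be reported, for example the Hodges–Lehmann shift with a 90% interval to match the 0.10 level.

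This option needs the least editing and keeps to the protocol. Its price is usually lower power than ANCOVA: in the base case 1 to 14 points, depending on the correlation.

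If the sponsor prefers ANCOVA as the main test, the synopsis and section 4.8.3.2 of the protocol must be amended to match. Either way, data collection and sample size do not change. The SAP needs revision in any case, because it still plans the cancelled interim analysis.
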